### **6.1.6.3 Reporting Adverse Events**

All AEs reported or observed during the study will be recorded on the AE page of the eCRF. Information to be collected includes drug treatment, dose, event term, time of onset, Investigator-specified assessment of severity and relationship to study drug, time of resolution of the event, seriousness, any required treatment or evaluations, and outcome. Adverse events resulting from concurrent illnesses, reactions to concurrent illnesses, reactions to concurrent medications, or progression of disease states must also be reported. All AEs will be followed to adequate resolution. The Medical Dictionary for Regulatory Activities (MedDRA) will be used to code all AEs.

Any medical condition that is present at the time that the patient is screened but does not deteriorate should not be reported as an AE. However, if it deteriorates at any time during the study, it should be recorded as an AE.

Any abnormal laboratory test results (hematology, clinical chemistry, or urinalysis) or other safety assessments (eg, ECGs, radiological scans, vital sign measurements), including those that worsen from baseline, deemed to be CS in the medical and scientific judgment of the Investigator are to be recorded as AEs or SAEs.

However, any CS safety assessments that are associated with the underlying disease, unless judged by the Investigator to be more severe than expected for the patient's condition, are not to be reported as AEs or SAEs.

Any AE that meets SAE criteria ([Section 6.1.6.1](#)) must be reported to the Sponsor and Medical Monitor immediately (ie, within 24 hours) after the time site personnel first learn about the event.

The Medical Monitor will be notified immediately (ie, within 24 hours) upon receipt of an SAE from the CRU using the following contact information:

[name]  
Senior Vice President, Clinical Development  
KBP Biosciences Co., Ltd.  
[name]  
[name]  
[contact]

In addition the SAE will be reported to DaVita Clinical Research within 24 hours as outlined in the site training materials and SAE reporting instructions. The immediately reportable SAE reports will be submitted to DaVita Clinical Research for documentation and handling and 24 hour monitoring of SAEs will be provided by the Investigator at the CRU as listed on the FDA 1572.

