### 6.1.4 12-Lead Electrocardiograms

Electrocardiogram parameters of ventricular rate, PQ or PR interval, QRS duration, QT interval (uncorrected), and QT interval corrected for heart rate according to Fridericia's formula (QTcF) will be performed at the timepoints specified in [Table 12-1](#) and [Table 12-2](#) for Part 1 and Part 2, respectively.

Electrocardiograms will be obtained with the patient remaining in a semi-recumbent position following 5 minutes of rest. If other procedures are scheduled at the same timepoint, the ECG should be obtained after vital sign measurements and/or before the scheduled blood draw. The allowable window for ECGs to be obtained with respect to their nominal timepoint is -60 minutes for predose ECGs and  $\pm 30$  minutes for postdose ECGs.

For all patients, ECGs will be reviewed, signed, and dated by the Investigator or a qualified designee. The ECGs will be classified as being one of three categories: normal, abnormal but not clinically significant (NCS), or abnormal and CS. All CS findings will be reported as AEs.

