## **6.1.6 Adverse Events**

### **6.1.6.1 Definitions of Adverse Events**

The Investigator is responsible for reporting all AEs that are observed or reported during the study, regardless of their relationship to study drug or their clinical significance.

An AE is defined as any untoward medical occurrence in a patient enrolled into this study regardless of its causal relationship to study drug. Patients will be instructed to contact the Investigator at any time after signing the ICF until the final end of study assessment if any symptoms develop.

A treatment-emergent AE (TEAE) is defined as any event not present before exposure to study drug or any event already present that worsens in either intensity or frequency after exposure to study drug.

An SAE is defined as any event that results in death, is immediately life threatening, requires inpatient hospitalization or prolongation of existing hospitalization, results in persistent or significant disability/incapacity, or is a congenital anomaly/birth defect. Important medical events that may not result in death, be life threatening, or require hospitalization may be considered SAEs when, based upon appropriate medical judgment, they may jeopardize the patient or may require medical or surgical intervention to prevent one of the outcomes listed in this definition. Examples of such medical events include allergic bronchospasm requiring intensive treatment in an emergency room or at home, blood dyscrasias or convulsions that do not result in inpatient hospitalization, or the development of drug dependency or drug abuse.

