## **6.2 Laboratory Analyses**

Any abnormal laboratory test results (hematology, clinical chemistry, or urinalysis) or other safety assessments (eg, ECGs, radiological scans, vital sign measurements), including those that worsen from baseline, felt to be CS in the medical and scientific judgment of the Investigator are to be recorded as AEs or SAEs.

However, any CS safety assessments that are associated with the underlying disease, unless judged by the Investigator to be more severe than expected for the patient's condition, are not to be reported as AEs or SAEs.

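### The exemption of disease-associated, clinically significant findings of expected severity from AE and SAE reporting conflicts with the ECG rule and has no exception for findings that meet the SAE criteria

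*Protocol*

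**What the plan says.** Four provisions of the protocol bear on this point.

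- **Section 6.1.4 (12-lead ECGs)** has each ECG classed as normal, abnormal but not clinically significant, or abnormal and clinically significant (CS). It then says: "All CS findings will be reported as AEs". There is no condition and no cross-reference.
- **Section 6.1.6.3 (Reporting Adverse Events)** first requires CS abnormal laboratory results and "other safety assessments (eg, ECGs, radiological scans, vital sign measurements") to be recorded as AEs or SAEs. The next paragraph takes out CS "safety assessments that are associated with the underlying disease, unless judged by the Investigator to be more severe than expected for the patient's condition". Section 6.2 repeats both paragraphs almost word for word, and its stated consequence is that such findings "are not to be reported as AEs or SAEs".
- **Section 6.1.6.1 (Definitions)** defines seriousness mainly by outcome: "An SAE is defined as any event that results in death, is immediately life threatening, requires inpatient hospitalization", and so on. It adds important medical events that may be considered serious on medical judgment, with examples such as "blood dyscrasias or convulsions that do not result in inpatient hospitalization". It has no exclusion for underlying disease.
- **The 24-hour rule in Section 6.1.6.3** opens with "Any AE that meets SAE criteria".

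**The concern.** Safety and tolerability form the first primary objective (Section 2.1), and every patient has severe chronic kidney disease or is on hemodialysis. Many abnormal ECG, potassium or other laboratory findings could plausibly be put down to the underlying disease, so the exemption is not a remote one.

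Two things look wrong. The site has opposing instructions for one class of ECG finding, and nothing says which prevails. The exemption also reaches SAEs, while its only way out is a judgment of severity relative to what the patient's condition would lead one to expect. Seriousness under Section 6.1.6.1 is a different test, and a finding can be expected for the disease and still meet it.

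At stake is the AE record with its severity and causality assessment and, for the serious case, prompt notification of the sponsor and medical monitor. The measured values themselves are not lost.

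**Working it through.** No figure in the protocol bears on this, so the check sets the rules side by side.

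**1. Does the exemption cover ECGs?** Yes. The paragraph just before it lists ECGs among the safety assessments, and the exemption uses the same term. Section 6.2 has the same pair of paragraphs.

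**2. Which CS ECG findings fall under opposing rules?**

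| CS ECG finding | Section 6.1.4 | Sections 6.1.6.3 and 6.2 |
|---|---|---|
| Not associated with the underlying disease | Report | Report |
| Associated, more severe than expected | Report | Report |
| Associated, not more severe than expected | Report | Do not report |

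Only the last row conflicts, and there the conflict is complete.

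**3. How often could that row arise?** Appendix 12.1 (Tables 12-1 and 12-2) schedules two postdose ECGs per patient, at 6 hours and at end of study. With 12 planned patients and no replacements, that is 2 × 12 = 24 scheduled postdose ECGs, plus any unscheduled ones. A finding must be CS, disease-associated and of expected severity to be caught. The protocol gives no rate for this.

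**4. Can a serious finding fall through?** Take a test finding that meets the SAE definition.

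- If it comes with a death, a hospitalization or another clinical event, that event is not itself a safety assessment. It stays reportable under Section 6.1.6.1, and Section 6.1.6.2 has patients asked about hospitalization at every visit.
- If the investigator judges the finding more severe than expected, the exemption does not apply and the finding is reported.
- If it is of expected severity and there is no separate clinical event, the exemption says it is neither an AE nor an SAE. The SAE definition can still be met through the life-threatening criterion or the important-medical-event clause, neither of which needs hospitalization. The 24-hour rule is worded for AEs that meet the SAE criteria, so it does not clearly bring back a finding already removed from AE reporting.

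The third branch is the gap.

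**5. What remains visible?** Section 7.7.2 lists investigator-identified ECG abnormalities, summarizes them by clinical significance, and summarizes laboratory data with out-of-range values flagged in listings. A finding in the gap would appear there without an AE entry.

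**The case against.** The strongest reply is that the reporting section supplies an ordinary exception to a general statement. Section 6.1.6.3 repeats the rule that CS findings are recorded and then qualifies it, and a sensible site would read Section 6.1.4 subject to that. The conflicting set is also narrow. Exclusion criteria 2, 9 and 10 screen out unsuitable cardiovascular disease, recent severe arrhythmia or infarction, and symptomatic heart failure. Conditions present at screening that do not deteriorate are not AEs in any case. On SAEs, a life-threatening finding would usually be judged more severe than expected, and the clause that contains the blood-dyscrasia example is permissive. Section 6.1.6.5 tells sites to report in doubt, Section 4.2.1 has all safety data reviewed, and serum potassium has its own repeat-test rule in Section 6.1.5.

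Most of this stands as a limit on size. It does not remove the conflict, because Section 6.1.4 says that all such findings are reported and does not point to the exemption. The report-if-in-doubt default does not clearly override an express instruction not to report.

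A reader might also infer three stronger points that the protocol does not support.

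- **All disease-associated CS findings are excluded.** They are not: those judged more severe than expected stay reportable.
- **Deaths or hospitalizations are suppressed.** They are not: they remain events under Sections 6.1.6.1 and 6.1.6.2.
- **The deterioration sentence is a further contradiction.** Section 6.1.6.3 says of a condition present at screening that "if it deteriorates at any time during the study, it should be recorded as an AE". That concerns a medical condition, while the exemption concerns safety assessments. The two can be read together: clinical worsening is reported, and an isolated expected value is not.

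**Conclusion.** The concern holds in a limited form. Sections 6.1.6.3 and 6.2 contradict Section 6.1.4 for CS ECG findings that are disease-associated and of expected severity. The exemption also reaches SAEs with no exception for seriousness, so a test finding that is serious but expected, without a separately reported clinical event, can miss AE entry and prompt SAE notification.

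The size is small and cannot be quantified from the document. One might note that a single patient classified differently moves an AE incidence by 1/6 in a part of 6 patients. That is true of any reclassified patient in a cohort of this size and is no evidence about this wording. The safety analysis is descriptive, and the protocol ties no decision rule to AE counts. The point should be corrected because it concerns a primary objective and the prompt reporting of serious findings, and because the correction is only wording. The conclusion assumes that the site follows the text as written and that no other document, such as the SAE reporting instructions mentioned in Section 6.1.6.3, settles the matter.

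**What to change.** 1. Reconcile Section 6.1.4 with Sections 6.1.6.3 and 6.2 so that one rule governs CS ECG findings. Either make Section 6.1.4 expressly subject to the exemption, or take ECG findings out of the exemption. Both remove the conflict.
2. Add to Sections 6.1.6.3 and 6.2: *This exception does not apply to any finding that meets the SAE criteria in Section 6.1.6.1.*

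The investigator's test of whether a finding is more severe than expected can stay. The change is wording in three sections and needs no new visit, sample or procedure. The downside is possibly a few more AE or SAE entries among the 12 planned patients.

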#### **6.1.6.4 Assessment of Severity**

The severity, or intensity, of an AE refers to the extent to which an AE affects the patient's daily activities. The intensity of the AE will be rated as mild, moderate, or severe using the following criteria:

Mild: These events require minimal or no treatment and do not interfere with the patient's daily activities.

Moderate: These events result in a low level of inconvenience or concern with the therapeutic measures. Moderate events may cause some interference with normal functioning.

Severe: These events interrupt a patient's usual daily activity and may require systemic drug therapy or other treatment. Severe events are usually incapacitating.

Changes in the severity of an AE should be documented to allow an assessment of the duration of the event at each level of intensity to be performed. Adverse events characterized as intermittent do not require documentation of onset and duration of each episode.

#### **6.1.6.5 Assessment of Causality**

The Investigator's assessment of an AE's relationship to study drug is part of the documentation process, but it is not a factor in determining what is or is not reported in the study. If there is any doubt as to whether a clinical observation is an AE, the event should be reported.

The relationship or association of the test article in causing or contributing to the AE will be characterized using the following classification and criteria:

Unrelated: This relationship suggests that there is no association between the study drug and the reported event.

Possible: This relationship suggests that treatment with the study drug caused or contributed to the AE, ie, the event follows a reasonable temporal sequence from the time of drug administration or follows a known response pattern to the study drug, but could also have been produced by other factors.

Probable: This relationship suggests that a reasonable temporal sequence of the event with drug administration exists and, based upon the known pharmacological action of the drug, known or previously reported adverse reactions to the drug or class of drugs, or judgment based on the Investigator's clinical experience, the association of the event with the study drug seems likely. The event disappears or decreases on cessation or reduction of the dose of study drug.

Definite: This relationship suggests that a definite causal relationship exists between drug administration and the AE, and other conditions (concurrent illness, progression/expression of disease state, or concurrent medication reaction) do not appear to explain the event. The event reappears or worsens if the study drug is re-administered.

### **6.1.6.6 Follow-Up of Patients Reporting Adverse Events**

All AEs must be reported in detail on the appropriate page of the eCRF and followed to satisfactory resolution, until the Investigator deems the event to be chronic or not CS, or until the patient is considered to be stable.

## **6.2 Laboratory Analyses**

Any abnormal laboratory test results (hematology, clinical chemistry, or urinalysis) or other safety assessments (eg, ECGs, radiological scans, vital sign measurements), including those that worsen from baseline, felt to be CS in the medical and scientific judgment of the Investigator are to be recorded as AEs or SAEs.

However, any CS safety assessments that are associated with the underlying disease, unless judged by the Investigator to be more severe than expected for the patient's condition, are not to be reported as AEs or SAEs.

### **6.3 Pregnancy**

Pregnancy is not regarded as an AE unless there is a suspicion that an investigational product may have interfered with the effectiveness of a contraceptive medication. Any pregnancy that occurs during study participation must be reported using a clinical study pregnancy reporting form. To ensure patient safety, each pregnancy must be reported to KBP Biosciences Co., Ltd. Within 2 weeks of learning of its occurrence. The pregnancy must be followed-up to determine outcome (including spontaneous miscarriage, elective termination, normal birth, or congenital abnormality) and status of mother and child, even if the patient was discontinued from the study. Pregnancy complications and elective terminations for medical reasons will be reported as an SAE. Spontaneous miscarriages must be reported as an SAE.

Any SAE occurring in association with a pregnancy, brought to the Investigator's attention after the patient has completed the study, and considered by the Investigator as possibly related to the study treatment, must be promptly reported to KBP Biosciences Co., Ltd.

## **7 Statistical and Analytical Plan**

### **7.1 Pharmacokinetic Variables**

#### **Part 1:**

The following PK parameters will be calculated using noncompartmental methods, whenever possible, based on plasma KBP-5074 concentrations:

PK Parameter	Definition
$C_{\max}$	maximum concentration
$t_{\max}$	time to maximum concentration
$AUC_{0-t}$	area under the concentration-time curve from time 0 until the last quantifiable concentration, calculated using the linear trapezoidal rule for increasing values, and the log trapezoidal rule for decreasing values
$AUC_{0-24h}$	area under the concentration-time curve from time 0 until 24 hours postdose, calculated using the linear trapezoidal rule for increasing values, and the log trapezoidal rule for decreasing values
$AUC_{0-\infty}$	area under the concentration-time curve extrapolated to infinity, calculated as: $AUC_{0-\infty} = AUC_{0-t} + C_t/\lambda z$
$\lambda z$	apparent terminal elimination rate constant
$t_{1/2}$	terminal elimination phase half-life, calculated as $\ln(2)/\lambda z$
$CL/F$	total body clearance, calculated as $Dose/AUC_{0-\infty}$
$V_z/F$	volume of distribution

## Part 2:

The following PK parameters will be calculated using noncompartmental methods, whenever possible, based on plasma KBP-5074 concentrations during the initial interdialytic interval:

During Interdialytic Interval	
PK Parameter	Definition
$C_{max}$	maximum concentration
$t_{max}$	time to maximum concentration
$AUC_{0-24h}$	area under the concentration-time curve from time 0 until 24 hours postdose, calculated using the linear trapezoidal rule for increasing values, and the log trapezoidal rule for decreasing values
$AUC_{0-44h}$	area under the concentration-time curve from time 0 until 44 hours postdose, calculated using the linear trapezoidal rule for increasing values, and the log trapezoidal rule for decreasing values
$AUC_{0-ti}$	area under the concentration-time curve from time 0 until the last timepoint during the first interdialytic interval, calculated using the linear trapezoidal rule for increasing values, and the log trapezoidal rule for decreasing values
$\lambda_z$	apparent terminal elimination rate constant
$t_{1/2}$	terminal elimination phase half-life, calculated as $\ln(2)/\lambda_z$

The following PK parameters will be calculated using noncompartmental methods, whenever possible, based on plasma KBP-5074 concentrations during dialysis and overall:

During Dialysis	
PK Parameter	Definition
Inlet $AUC_{t0-t1}$	area under the concentration-time curve from start of dialysis ( $t_0$ ) to the end of dialysis ( $t_1$ ) based on inflow concentrations. AUC will be calculated using the linear trapezoidal rule for increasing values, and the log trapezoidal rule for decreasing values
Outlet $AUC_{t0-t1}$	area under the concentration-time curve from start of dialysis ( $t_0$ ) to the end of dialysis ( $t_1$ ) based on outflow concentrations. AUC will be calculated using the linear trapezoidal rule for increasing values, and the log trapezoidal rule for decreasing values.
Outlet:Inlet Concentration Ratio	ratio of outflow to inflow concentrations based on time-matched inflow and outflow samples
Outlet:Inlet AUC Ratio	ratio of Outlet $AUC_{t0-t1}$ to Inlet $AUC_{t0-t1}$
$CL_{D, Recovery}$	estimated hemodialysis recovery clearance, where: $CL_{D, Recovery} = \text{Amount Recovered in Dialysate} / \text{Inlet } AUC_{t0-t1}$

$CL_D$	estimated hemodialysis clearance, where: $CL_D = Q * (C_i - C_o) / C_i$ $Q$ – Inlet blood flow, $C_i$ – Inlet concentration (arterial), and $C_o$ – Outlet concentration (venous)
$ER_D$	hemodialysis extraction ratio, where: $ER_D = (C_i - C_o) / C_i$ $C_i$ – Inlet concentration (arterial) and $C_o$ – Outlet concentration (venous)
$\lambda_z$	apparent terminal elimination rate constant, as data permit
$t_{1/2}$	terminal elimination phase half-life, calculated as $\ln(2) / \lambda_z$ , as data permit

Overall	
PK Parameter	Definition
$C_{max}$	maximum concentration
$t_{max}$	time to maximum concentration
$AUC_{0-t}$	area under the concentration-time curve from time 0 until the last quantifiable concentration, calculated using the linear trapezoidal rule for increasing values, and the log trapezoidal rule for decreasing values
$AUC_{0-\infty}$	area under the concentration-time curve extrapolated to infinity, calculated as: $AUC_{0-inf} = AUC_{0-t} + C_t / \lambda_z$
$\lambda_z$	apparent terminal elimination rate constant
$t_{1/2}$	terminal elimination phase half-life, calculated as $\ln(2) / \lambda_z$
$CL/F$	total body clearance, calculated as $Dose / AUC_{0-\infty}$
$V_z/F$	volume of distribution

Pharmacokinetic parameters will be calculated using a validated software program such as WinNonlin version 6.4 or higher. Additional PK parameters may be calculated or compartmental analysis may be performed, as appropriate, to fully characterize available data.

Additional details regarding the PK parameter calculations are presented in the Statistical Analysis Plan (SAP).

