To address the long elimination half-life of KBP-5074, the current study will evaluate the PK following a single oral dose of KBP-5074. This dose will be administered following a dialysis session in Part 2. This single-dose approach has been used in the PK assessment for compound with relative long  $t_{1/2}$  in patients requiring HD. Pharmacokinetic assessments will be performed during the subsequent interdialytic interval (approximately 44 hours), during the following dialysis session (approximately 4 hours), and through 312 hours postdose.

This approach will allow for a limited estimation of KBP-5074 PK parameters during the interdialytic period. In addition it will allow for estimation of parameters related to hemodialysis clearance of KBP-5074 (e.g., hemodialysis extraction ratio and hemodialysis clearance, hemodialysis recovery clearance). Finally, this approach will provide a full single-dose PK profile of KBP-5074 collected over multiple dialysis sessions and interdialytic intervals. This full PK profile can be compared to previous single-dose profiles in healthy patients and renally-impaired patients not undergoing hemodialysis.

Safety and tolerability will be assessed through physical examination findings, vital signs, 12-lead ECGs, clinical laboratory findings, and monitoring of AEs. The PK of KBP-5074 in

Part 2 will be assessed during the interdialytic period, during dialysis, and overall by obtaining blood samples, dialysate samples, and by calculating appropriate PK parameters.

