### **6.1.1 Body Height, Weight, and BMI**

At Screening, body height (centimeters) and weight (kilograms) will be measured, and BMI will be calculated ( $\text{BMI} [\text{kg}/\text{m}^2] = \text{body weight} [\text{kg}] / \text{height}^2 [\text{m}^2]$ ).

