### **Pharmacokinetic Blood Collection and Processing**

Blood samples for the PK analysis of KBP-5074 will be collected at the timepoints specified in [Table 12-1](#) and [Table 12-2](#) for Part 1 and Part 2, respectively. In Part 1, all blood samples will be taken by either direct venipuncture or an indwelling cannula inserted in a forearm vein. In Part 2, blood samples will be taken by either direct venipuncture or an indwelling cannula inserted in a forearm vein during the interdialytic interval and following HD. While HD patients are undergoing dialysis treatment, blood samples must be drawn from the predialyzer (inlet [arterial line]) and postdialyzer (outlet [venous line]) at the timepoints specified in [Table 12-2](#). Blood samples will be collected into labeled tubes containing sodium heparin.

In Part 2, serial PK samples will initially be collected during the postdose interdialytic interval (through approximately 44 hours postdose). Approximately 44 hours following dose administration, the next dialysis session will occur. Serial blood samples (inlet and outlet) as well as dialysate samples will be collected for the duration of this dialysis session (from approximately 44 hours postdose through approximately 48 hours postdose). Additional serial PK samples will be collected following this dialysis session through 312 hours postdose (see [Table 12-2](#)).

Immediately after the sample is collected, the tube should be gently inverted 5 to 8 times to thoroughly mix the anticoagulant and then placed upright in a cryoblock or test tube rack surrounded by ice until centrifugation. Samples will be centrifuged at  $1500 \times g$  for 10 minutes at approximately  $4^{\circ}\text{C}$  within 30 minutes of collection. The resultant plasma will be divided into 2 equal aliquots, placed in individual cryovials, and immediately frozen at  $-70^{\circ}\text{C}$  or colder within 1 hour of collection. The samples will be kept frozen at  $-70^{\circ}\text{C}$  or colder pending shipment to the bioanalytical laboratory. Additional details, including the acceptance of shipments by the bioanalytical laboratory, will be provided in a separate laboratory manual.

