### **Dialysate Collection and Processing**

Dialysate will be collected for HD patients in Part 2 only. Pooled dialysate samples will be collected during specific intervals as specified in [Table 12-2](#). Sample aliquots of the dialysate will be collected and frozen at  $-70^{\circ}\text{C}$  or colder and the total volume of the collected dialysate will be recorded. The samples will be kept frozen at  $-70^{\circ}\text{C}$  or colder pending

shipment to the bioanalytical laboratory. Additional details, including the acceptance of shipments by the bioanalytical laboratory, will be provided in a separate laboratory manual. DaVita Clinical Research will document the make and model of the dialyzer, blood flow, and dialysate flow for this study.

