Patient should be resting in a semi-recumbent position for at least 5 minutes prior to ECG.

Blood pressure, heart rate, respiratory rate and oral temperature will be measured in patients in a semi-recumbent position for at least 5 minutes.

Clinical laboratory samples include: hematology, clinical chemistry, liver function, and urinalysis.

Dosing will be based on the post dialysis weight from the last dialysis session prior to dosing.

Blood samples for the determination of KBP-5074 concentrations and PK analysis will be collected relative to dose administration as follows (All PK samples will be collected within ±5 minutes of the nominal time unless otherwise specified):

- During the interdialytic interval (using a venous stick or cannula) immediately predose (at time 0 [-5 min]; collected immediately prior to dosing, but following the termination of a previous dialysis session), 2, 4, 6, 8, 10, 12, 18, and 24 hours postdose;
- During the second HD session at 44 (immediately prior to HD [using a venous stick or cannula; -5 min] and 5 minutes after the start of HD [inlet {arterial; ±1 min} and outlet {venous; ±1 min} samples]), 44.25, 44.5, 46, and 47 hours postdose, and at the end of the second HD session;
- Following dialysis (using a venous stick or cannula) at 48.5, 49, 50, 52, 72, 96, 120, 168, 216, 264, and 312 hours postdose.

Cumulative dialysate will be collected and weight/volume determined for the following intervals: 44 to 44.5 hours, 44.5 to 45 hours, 45 to 46 hours, 46 to 47 hours, and 47 to 48 hours postdose. The dialysate collection will end at the end of dialysis (rather than at 48 hours) if a patient has dialysis for <4 hours. An additional sample may be collected until the end of dialysis for sessions lasting longer than 4 hours. The cumulative volume of dialysate collected during each interval will be documented. A 25 mL aliquot will be collected at the end of each interval for determination of KBP-5074 concentration.

Serum and plasma samples for biomarkers (aldosterone and serum potassium) will be collected at the following time points (All biomarker samples will be collected within  $\pm 5$  minutes of the nominal time unless otherwise specified): predose (at time 0 [-5 min], collected immediately prior to dosing) and 2, 6, 12, 24, 48, 72, 96, 120, 168, 216, 264, and 312 hours post dose.

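### CL_D and ER_D are defined without a fluid-removal term, so both are biased low and turn negative when true dialysis clearance is below the ultrafiltration rate

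*Protocol*

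**What the plan says.** The During Dialysis table of Protocol Section 7.1 (Part 2) gives two closed formulas:

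- CL_D: "estimated hemodialysis clearance, where: $CL_D = Q * (C_i - C_o) / C_i$ $Q$ – Inlet blood flow".
- ER_D: "hemodialysis extraction ratio, where: $ER_D = (C_i - C_o) / C_i", with the same inlet and outlet concentrations.

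The same table lists the Outlet:Inlet concentration ratio, the Outlet:Inlet AUC ratio, and CL_D,Recovery. The last is the amount recovered in dialysate divided by inlet AUC.

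For the session itself, Section 6.1.5.1 (Dialysate Collection and Processing) says that these items will be documented: "make and model of the dialyzer, blood flow, and dialysate flow for this study". Ultrafiltration is not among them and is not mentioned elsewhere in the protocol. Table 12-2, footnote 8, adds: "The cumulative volume of dialysate collected during each interval will be documented".

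On weight, Section 6.1.1 says "At Screening, body height (centimeters) and weight (kilograms) will be measured", and the weight row of Table 12-2 is marked only at Screening. Footnote 6 of that table refers to a post-dialysis weight, but from the session before dosing.

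Section 3.1.1 states that the design will allow "estimation of parameters related to hemodialysis clearance of KBP-5074", and names extraction ratio, hemodialysis clearance and recovery clearance as examples. PK during the dialysis session is part of a primary objective (Section 2.1).

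**The concern.** A dialysis session normally removes fluid as well as solute. Less plasma water then leaves the dialyzer than enters it, and whatever drug remains is concentrated. The outlet concentration rises for a reason unrelated to drug removal, and a formula that compares only the two concentrations reads this as negative removal.

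The error matters most when dialysis clears little of the drug. In that case the sign of CL_D and ER_D can be wrong. The Outlet:Inlet ratios can exceed 1 and be mistaken for a sampling or assay fault. CL_D will also disagree with CL_D,Recovery for an arithmetic reason. These are quantities that the design rationale says the study will estimate.

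**Working it through.** The plan states no numerical value for these parameters, so there is no figure to reproduce. The check is a mass balance followed by a range.

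**Inputs from the protocol.** The two formulas (Section 7.1); a session of about 4 h (Section 3.1.1); AUC to infinity of 678.4 ng·h/mL after 0.5 mg in healthy subjects (Section 1.3).

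**Inputs assumed, because the protocol gives none.** Q 300–500 mL/min, with Q the flow that matches the measured concentrations; Quf 5–15 mL/min, which over 240 min is 1.2–3.6 L. The mid case is Q 400, Quf 10.

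**Mass balance.** Drug in = drug out in blood + drug removed:

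Q × Ci = (Q − Quf) × Co + CL × Ci, so Co/Ci = (Q − CL)/(Q − Quf).

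**Put into the planned formulas.**

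- ER_D = 1 − Co/Ci = (CL − Quf)/(Q − Quf)
- CL_D = Q × (CL − Quf)/(Q − Quf)
- Bias of CL_D = CL_D − CL = −Quf × (Q − CL)/(Q − Quf)

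The bias is negative for every CL below Q. Both parameters are zero at CL = Quf and negative below it. Co/Ci exceeds 1 under the same condition, so the two Outlet:Inlet ratios do too.

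**Drug not removed at all (CL = 0).**

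- Q 500, Quf 5: CL_D = 500 × (−5)/495 = −5.1 mL/min; ER_D = −5/495 = −1.0%
- Q 300, Quf 15: CL_D = 300 × (−15)/285 = −15.8 mL/min; ER_D = −15/285 = −5.3%

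**Mid case, CL_D = 400 × (CL − 10)/390.**

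| True CL (mL/min) | Reported CL_D | Relative bias |
|---|---|---|
| 0 | −10.3 | – |
| 5 | −5.1 | sign reversed |
| 10 | 0 | −100% |
| 25 | 15.4 | −38% |
| 50 | 41.0 | −18% |
| 100 | 92.3 | −8% |
| 150 | 143.6 | −4% |

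**Scale.** Healthy-subject CL/F = 500,000 ng / 678.4 ng·h/mL = 737 mL/h = 12.3 mL/min. The offset at zero clearance is of the same order. This is an apparent oral clearance in a different population, so it serves only as a yardstick.

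**Corrected formula.** CL_D = [Q × Ci − (Q − Quf) × Co]/Ci. Mid case, true CL 0: Co/Ci = 400/390, so CL_D = 400 − 390 × 400/390 = 0. True CL 25: Co/Ci = 375/390, so CL_D = 400 − 375 = 25. It returns the true value when Q matches the concentrations and Quf is correct.

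**Can Quf be recovered from the planned data?** Only poorly. At an assumed dialysate flow of 500–800 mL/min, a 1% flow error is 5–8 mL/min, as large as the lower half of the assumed Quf range.

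**The case against.** The strongest reply is that little depends on this. The study is descriptive, with no formal sample size (Section 7.4) and no decision rule on CL_D. CL_D,Recovery uses neither outlet concentration nor blood flow, and it is planned from dialysate collected in intervals. At high clearance the bias is a few percent. Section 7.1 also leaves further calculation detail to the SAP, and Section 7.7 allows the SAP to modify the plan.

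Most of this stands and limits the weight of the point. The SAP argument stands only in part. The SAP is not at hand and could add a term, but the protocol prints the formulas explicitly, and a later correction needs a fluid-removal figure that the listed session data do not include.

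A reader might infer more than the documents support:

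- **That negative values will occur, or that dialysis clearance cannot be estimated.** Neither the drug's dialysis clearance nor the ultrafiltration rates are in the protocol. Assay error can move single values either way near zero, and CL_D,Recovery remains available.
- **That weight is recorded only at Screening.** Footnote 6 of Table 12-2 relies on a post-dialysis weight. It belongs to the session before dosing, so it does not give fluid removal in the studied one.
- **That fluid removal will go unrecorded.** Section 6.1.5.1 lists what will be documented; it does not exclude other session data.
- **That using inlet blood flow with plasma data is itself an error.** The parameters are "based on plasma KBP-5074 concentrations during dialysis and overall", and the assayed matrix is confirmed in Section 6.1.5.1: "The resultant plasma will be divided into 2 equal aliquots". This mis-scales CL_D only if the blood:plasma ratio differs from 1. No ratio is given, so neither the existence nor the direction of an error can be shown.

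**Conclusion.** The point holds as a minor to moderate correction. As written, CL_D and ER_D are biased low whenever net fluid is removed and clearance is below Q. For error-free, time-matched samples they are negative whenever true dialysis clearance is below Quf. That sign rule is algebra and does not depend on the assumed rates.

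The sizes do depend on them: about −5 to −16 mL/min for an undialysed drug over the assumed range, falling to about 8% at a true clearance of 100 mL/min in the mid case. No trial decision changes. What is at stake is the correct reading of CL_D, ER_D and the Outlet:Inlet ratios, chiefly if the drug is poorly dialysed.

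**What to change.** 1. In Section 6.1.5.1, add ultrafiltration volume or rate for the studied session to the items documented.
2. In Section 7.1, set CL_D = [Q × Ci − (Q − Quf) × Co]/Ci and ER_D = CL_D/Q, and report both beside CL_D,Recovery.
3. Note that an Outlet:Inlet ratio above 1 can reflect fluid removal alone, and that the corrected ER_D no longer equals 1 minus the concentration ratio.
4. State whether Q is blood or plasma flow, and that it should match the plasma concentrations given the known blood:plasma partition. If the partition is unknown, say so as a limitation. The corrected formula is exact only with a matched Q, and ER_D, which contained no flow before, now depends on it.

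The cost is a change to two formula entries, a few sentences, and one added data item for a single session in each Part 2 patient. No extra patients or blood samples are needed. The data item has to be in place before the Part 2 sessions are run, because the planned dialysate volumes are too imprecise to supply it afterwards.
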